2.4.5 Association of ADA with selected efficacy endpoints

Scatter plots will be used to display the correlations of immunogenicity (ADA titers and NAb) and change from baseline at week 25 for selected efficacy endpoints including 6MWT (total distance walked in meter), FVC (% predicted) upright, FVC (% predicted) supine, MIP (% predicted) upright, MEP (% predicted) upright, GMFM-88, QMFT, Pompe-PEDI Functional Skills Scale: Mobility Domain, CK, LVM Z-score, LVMI, Hex4, GAA genotyping, CRIM status, GAA enzyme activity and [REDACTED].

2.4.6 Association of ADA with safety

Selected safety parameters (AEs, SAEs, IARs and potential immune complex mediated reactions) will be summarized by ADA and NAb response categories.

2.4.7 Analyses of pharmacokinetic variables

PK exposures (C_{max} and AUC_{0-last}) for avalglucosidase alfa will be determined using non-compartmental analysis. If data allow, total body clearance of a drug (CL), and V_{ss} will be determined. If data do not lend to non-compartmental analysis, model-based approaches such as nonlinear mixed effects modeling may be used. Values will be reported for individual patients and summarized using descriptive statistics by study week and time point as appropriate.

The results will be presented by dose levels among avalglucosidase alfa patients in the PK population.

PK parameters for individual patients will be derived from population PK analysis using the data from this study pooled with other studies if necessary. The population PK results will be documented in a separate report.

To evaluate the effect of immunogenicity on the pharmacokinetics of avalglucosidase alfa, pre-dose IgG titer for each patient will be presented graphically with respect to PK parameter.

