- o Biochemistry assessments only for participants treated with alglucosidase alfa. Sampling is not required for Stage 2 - Cohort 3 participants randomized to treatment with alglucosidase alfa.
- p Serum samples are collected pre-infusion at each time point. Additional samples may be taken if clinically indicated in the event of IARs. Stage 2 Cohort 3 patients receiving alglucosidase alfa treatment do not require sampling of anti- alglucosidase alfa antibodies and neutralizing antibodies in anti-alglucosidase alfa antibody positive patients at Day 8, Week 5, Week 9, Week 13, Week 17, Week 21.
- q Pharmacokinetic sampling schedule: prior to infusion; at the end of infusion; and 2, 4, 6, and 8 hours after the end of infusion at Day 1 and Week 25 and prior to infusion and 2 hours after the end of infusion at Week 13; additionally in the 40 mg/kg dose cohort 12 to 16 hours after the end of infusion at Day 1 and Week 25. For Stage 2 - Cohort 3 participants randomized to treatment with alglucosidase alfa, sampling of

avalglucosidase alfa pharmacokinetics is not required at Day 1, Week 13 and Week 25. Pharmacokinetic blood samples are to be collected within 15 minutes of scheduled time: predose and all samples immediately following the end of the infusion through 8 hours post infusion.

r [REDACTED]

s Blood samples will be obtained as blood volume permits and will not exceed the blood volume collection limit of < 7 mL/kg over an 8-week period. Sampling is prioritized for safety labs (hematology, biochemistry, ADA) and PK [REDACTED]
[REDACTED]

t Time points are suggested time points.

u In the event patient requires ventilator support (invasive or non-invasive) at any time during study treatment the patient will be asked to complete a daily ventilator use diary. On a biweekly basis, the periods of ventilator use/day (daytime, nighttime, both) will be reported by the Investigator based on the ventilator use diary.

v Patients included in Cohort 3 on the basis of sub-optimal clinical response documented by motor scale and/or clinical development evaluation tools other than GMFM-88 or Pompe-PEDI will undergo assessment with those tools in combination with the prescribed/planned testing at screening/baseline and Week 25.

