9.2 SECONDARY ENDPOINTS

9.2.1 Pharmacokinetics

9.2.1.1 *Sampling time*

Blood samples for full evaluation of avalglucosidase alfa PK will be collected before and after infusions on V2 (Day 1) and V15 (Week 25) for participants who are treated with avalglucosidase alfa starting at Day 1. For participants in Stage 2 – Cohort 3 who are randomized to receive treatment with alglucosidase alfa at current stable dose during the Treatment Period and who switch to avalglucosidase alfa in the Extension Period, full PK profiles will be sampled on V16 (Week 27) and V28 (Week 49). Sampling times are as follows: predose (prior to infusion); at the end of the infusion; and at 2, 4, 6, and 8 hours after the end of infusion. PK samples will also be taken prior to infusion and at 2 hours after the end of infusion at V9 (Week 13), or at V22 (Week 37) for the avalglucosidase alfa switch patients. For patients in the 40 mg/kg dose cohorts, additional blood samples will be collected at 12 to 16 hours after infusions on V2 (Day 1) and V15 (Week 25), or on V16 (Week 27) and V28 (Week 49) for the avalglucosidase alfa switch patients (see [Table 1](#)).

Table 1 – PK sampling time

Visit	Cohort 1 patients	Cohort 2 patients	Cohort 3 patients randomized to avalglucosidase alfa	Cohort 3 patients randomized to alglucosidase alfa and switching to avalglucosidase alfa in the extension period
V2 (D1)	Predose; end of infusion; 2, 4, 6 and 8 h after end of infusion	Predose; end of infusion; 2, 4, 6, 8 and 12-16 h after end of infusion	Predose; end of infusion; 2, 4, 6, 8 and 12-16 h after end of infusion ^a	
V9 (W13)	Predose and 2 h after end of infusion	Predose and 2 h after end of infusion	Predose and 2 h after end of infusion	
V15 (W25)	Predose; end of infusion; 2, 4, 6 and 8 h after end of infusion	Predose; end of infusion; 2, 4, 6, 8 and 12-16 h after end of infusion	Predose; end of infusion; 2, 4, 6, 8 and 12-16 h after end of infusion	
V16 (W27)				Predose; end of infusion; 2, 4, 6, 8 and 12-16 h after end of infusion ^a
V22 (W37)				Predose and 2 h after end of infusion
V28 (W49)				Predose; end of infusion; 2, 4, 6, 8 and 12-16 h after end of infusion ^a

a If the cohort 3 dose of avalglucosidase alfa is 20 mg/kg qow, the 12-16 hours after the end of infusion sample will not be taken.

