9.2.1.3 Bioanalytical method

Plasma samples will be analyzed using validated, sensitive and specific bioanalytical methods, namely, a fluorometric assay using a 4-methylumbelliferyl- α -D-glucoside (4-MUG) substrate to detect avalglucosidase alfa activity.

The lower limit of quantitation (LLOQ) is 12.0 ng/mL or 0.0120 μ g/mL.

9.2.1.4 **Pharmacokinetics parameters**

The following PK parameters will be determined for avalglucosidase alfa based on non-compartmental analysis. The parameters will include maximum plasma concentration observed (C_{max}), time to achieve maximum plasma concentration (t_{max}), area under the curve from time 0 to time of the last quantifiable concentration (AUC_{0-last}), and terminal half-life ($t_{1/2z}$). If data permit, other parameters including total body clearance of a drug from plasma (CL) and volume of distribution (Vd) will be included. The definitions of the PK parameters are presented in [Table 2](#).

Table 2 - List of pharmacokinetic parameters and definitions

Parameters	Drug/Analyte	Matrix	Definition/Calculation
C_{max}	avalglucosidase alfa	Plasma	Maximum plasma concentration observed
t_{max}	avalglucosidase alfa	Plasma	Time to achieve maximum plasma concentration
AUC_{0-last}	avalglucosidase alfa	Plasma	Area under the plasma concentration versus time curve from time 0 to time of the last quantifiable concentration
$t_{1/2z}$	avalglucosidase alfa	Plasma	terminal half-life
CL	avalglucosidase alfa	Plasma	Total body clearance of a drug from the plasma
Vd	avalglucosidase alfa	Plasma	Volume of distribution

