11.4.4 Analyses of pharmacokinetic and pharmacodynamic variables

The list of PK parameters is listed in [Section 9.2.1.4](#).

PK exposures (C_{max} , $AUC_{0\text{-last}}$ and $t_{1/2z}$) for avalglucosidase alfa may be determined using non-compartmental analysis. If data allow, total body clearance of a drug (CL) and Vd will be determined. If data do not lend to non-compartmental analysis, model-based approaches such as nonlinear mixed effects modeling may be used. Values will be reported for individual subjects and summarized using descriptive statistics by study week as appropriate.

To evaluate the effect of immunogenicity on the PK of avalglucosidase alfa, predose IgG and neutralizing antibody titers for each patient will be analyzed graphically with respect to PK parameter. If relationships are apparent, further quantitative/statistical analysis may be performed (eg, statistical significance, correlation coefficients).

Pharmacodynamic endpoints as described in [Section 9.3.2](#) will be summarized using descriptive statistics at each scheduled study visit. Observed measurements as well as change from baseline will be summarized. If a linear trend in the change of a PD endpoint is observed, longitudinal model may be employed to model change from baseline over time. In addition, 95% confidence intervals of changes will be presented.

Urine Hex4 levels normalized by creatinine will be summarized using descriptive statistics at each scheduled study visit. Observed measurements as well as change from baseline will be summarized. If a linear trend in the change of urine Hex4 levels is observed, a longitudinal model may be employed to model change from baseline over time. In addition, 95% confidence intervals of changes will be presented.

Correlation between PK endpoints and Hex4 levels may be explored as appropriate.

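### The SAP's PK sections omit terminal half-life and the neutralising-antibody analysis, and name only AUC0-last, whose last scheduled sample differs by dose, so by-dose exposure may be distorted

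*SAP*

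**What the plan says.** **Parameters.** The protocol's endpoint list (Clinical Trial Summary), section 9.2.1.4 with its Table 2, and section 11.4.4 all include terminal half-life (t1/2z). SAP 2.1.5 lists Cmax, tmax, AUC0-last, CL and Vd. SAP 2.4.7 says "PK exposures (C_{max} and AUC_{0-last}) for avalglucosidase alfa will be determined using non-compartmental analysis", with CL and Vss to follow if the data allow. Neither SAP section mentions half-life, and neither document names AUC0-inf.

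**Sampling.** Protocol 9.2.1 schedules full profiles before dosing, then "at the end of the infusion; and at 2, 4, 6, and 8 hours after the end of infusion". It adds: "For patients in the 40 mg/kg dose cohorts, additional blood samples will be collected at 12 to 16 hours after infusions". A footnote to protocol Table 1 says: "If the cohort 3 dose of avalglucosidase alfa is 20 mg/kg qow, the 12-16 hours after the end of infusion sample will not be taken". Protocol Table 2 ends AUC0-last at the last quantifiable concentration, and section 9.2.1.3 sets the lower limit of quantitation (LLOQ) at 12.0 ng/mL.

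**Presentation.** SAP 2.4.7: "The results will be presented by dose levels among avalglucosidase alfa patients in the PK population". It also plans individual parameters from a population PK analysis, documented in a separate report.

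**Immunogenicity and PK.** Protocol 11.4.4: "predose IgG and neutralizing antibody titers for each patient will be analyzed graphically with respect to PK parameter". SAP 2.4.7 keeps pre-dose IgG titre only.

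**The concern.** Characterising the PK of avalglucosidase alfa is a secondary objective. Two pieces of PK work that the current protocol plans have no counterpart in the SAP, so a programmer following the SAP would not produce them.

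The neutralising-antibody gap has a particular edge. The PK assay detects enzyme activity (protocol 9.2.1.3), and NAb testing covers inhibition of enzyme activity as well as uptake (protocol 9.1.1.7, SAP 2.1.3.8). An activity-inhibiting antibody could in principle affect the measured value itself, which makes NAb status a natural variable to set against PK.

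The third issue is comparability. If the areas summarised side by side for 20 and 40 mg/kg stop at different times, part of the difference between them reflects the sampling schedule. Whether that part is trivial or not depends on half-life, the parameter that the SAP leaves out.

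**Working it through.** **1. Half-life: comparing the versions.** SAP 1.5 bases the SAP on a protocol dated 27 July 2018. Protocol 17.4.2 shows that t1/2z was added by amended protocol 02 of 24 March 2020, on the ground that it was tested but not presented. The SAP omission therefore fits a version lag, and the two documents now disagree.

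**2. Neutralising antibodies: where they appear.**

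| Analysis | Protocol | SAP |
|---|---|---|
| Antibodies against PK | IgG and NAb (11.4.4) | IgG only (2.4.7) |
| NAb listings and incidence | listings (11.4.2.4) | listings; incidence for uptake, activity and both (2.4.4.7) |
| NAb with efficacy | not specified | scatter plots (2.4.5) |
| NAb with safety | not specified | by response category (2.4.6) |

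Only the PK row loses NAb. SAP 1.6 says that the NAb assessment was simplified, and SAP 2.1.3.8 makes it positive or negative. Neither says that NAb was removed from the PK analysis.

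**3. Size of the interval effect.** The plan has no figure to reproduce. It gives no half-life, no expected concentration and no infusion length in hours; protocol 8.1 says only that length depends on dose.

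Assumptions:
- one compartment, linear PK, the same half-life at both doses
- constant-rate infusion of T = 4 h at 20 mg/kg and T = 7 h at 40 mg/kg
- every scheduled sample quantifiable

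With k = ln2/half-life, the share of AUC0-inf lying beyond s hours after end of infusion is

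f = [(1 − exp(−kT))/(kT)] × exp(−ks).

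The relative error in the 40:20 AUC0-last ratio is (1 − f40)/(1 − f20) − 1.

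Example at a half-life of 3 h (k = 0.231):
- f20 (s = 8) = 0.6526 × 0.1575 = 0.103
- f40 (s = 12) = 0.4956 × 0.0625 = 0.031
- f40 (s = 16) = 0.4956 × 0.0248 = 0.012
- error = 0.969/0.897 − 1 = 8.0% to 0.988/0.897 − 1 = 10.1%

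| Half-life | Missed at 20 mg/kg | Missed at 40 mg/kg (16 h to 12 h) | 40:20 ratio too high by | With both cut at 8 h |
|---|---|---|---|---|
| 1 h | 0.1% | <0.01% | 0.1% | 0.05% |
| 1.5 h | 1.1% | 0.02-0.12% | 1.0-1.1% | 0.4% |
| 2 h | 3.4% | 0.15-0.59% | 2.9-3.4% | 1.1% |
| 3 h | 10.3% | 1.2-3.1% | 8.0-10.1% | 2.8% |
| 4 h | 18.0% | 3.6-7.2% | 13.2-17.6% | 4.3% |
| 6 h | 31.8% | 10.8-17.1% | 21.5-30.8% | 6.7% |

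Other infusion lengths (4/4, 3/5 and 5/8 h) give 2.5-3.9% at a 2 h half-life and 6.9-11.2% at 3 h.

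The last column is not zero because the assumed infusions differ in length, so a cut 8 h after end of infusion leaves different tails.

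**4. LLOQ check.** A sample s hours after end of infusion is quantifiable only if the end-of-infusion concentration exceeds 0.012 × 2^(s/half-life) µg/mL. At a 1 h half-life that is 3.1 µg/mL for s = 8, 49 for s = 12 and 786 for s = 16. With fast elimination the late 40 mg/kg sample may fall below LLOQ, and the two areas then end closer together. The 8 h and 12-16 h limits are therefore the latest possible ends of AUC0-last.

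**The case against.** The best defence has four parts.

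- **AUC0-last is not the only route to exposure.** SAP 2.4.7 plans population PK and allows mixed-effects modelling where non-compartmental analysis fails. Such models do not need a common last sample. This stands, and it lowers the stakes. However, that work goes to a separate report, and the SAP does not say that it will deliver half-life, AUC0-inf or a NAb assessment.
- **No dose-proportionality test is planned.** PK is summarised descriptively, and Stage 1 has at least 5 patients per cohort. This also stands, but the areas will still be read side by side.
- **NAb titres no longer fit a positive/negative assessment.** Agreed. The remedy is a display by NAb status. It is also true that the protocol calls the PK assay validated and specific and reports no NAb interference, so interference is an inference.
- **The protocol's own wording is soft.** Section 11.4.4 says that the exposures, half-life included, may be determined. Section 9.2.1.4, however, commits to them and qualifies only CL and Vd.

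A reader might go further and infer any of the following, none of which the documents support:

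- *By-dose exposure is biased.* The direction follows from the schedule under the assumptions above, but the size is unknown and could be negligible.
- *CL at 20 mg/kg will be overstated.* Nothing says that CL is computed from AUC0-last.
- *The SAP abandoned NAb or a whole secondary endpoint.* NAb is missing only from the PK analysis, and half-life is one parameter among several that are still analysed.

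Vd in SAP 2.1.5 against Vss in 2.4.7 is a wording point.

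**Conclusion.** Two mismatches between protocol and SAP are established from the text: t1/2z has no place in SAP 2.1.5 or 2.4.7, and the protocol's NAb-against-PK analysis is missing from SAP 2.4.7.

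The third part is a conditional risk. The only area named has a last scheduled sample that depends on dose, and the 40:20 ratio may be inflated by anything from about 1% (half-life 1.5 h) to 13-18% (4 h). These figures rest on the assumed one-compartment model and infusions of 4 h and 7 h. The missed share at 20 mg/kg passes 5% only above a half-life of about 2.2-2.4 h (infusions of 3-5 h).

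All PK analyses are descriptive, so no alpha or power is affected. Severity is minor to moderate. It is worth correcting because the correction is cheap.

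**What to change.** In SAP 2.1.5 and 2.4.7:

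1. Add t1/2z, to match the current protocol.
2. Plot PK parameters by NAb status (positive or negative, with activity inhibition and uptake inhibition shown separately) alongside IgG titre.
3. Report AUC0-inf with the percent extrapolated, and state that non-compartmental CL and volume are based on it. Keep AUC0-last as planned.
4. For the by-dose display, add an AUC to 8 h after end of infusion in every avalglucosidase alfa patient. This reduces the difference without removing it (about 2.8% remains at a 3 h half-life), so it supplements AUC0-inf.
5. Use one volume term in both sections.

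The cost is SAP wording and a few derived parameters from samples already scheduled, with no new visits or blood draws. The drawback is that AUC0-inf may not be reportable where the extrapolated fraction is large. At 20 mg/kg that fraction would exceed 20% only above a half-life of about 4.1-4.5 h, under assumed infusions of 3-5 h.

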2.4.8 Analyses of efficacy endpoints

To evaluate the effect of switching to avalglucosidase alfa after having received alglucosidase alfa at current stable dose, comparative assessment on a composite score and several other efficacy endpoints will be conducted using the mITT population.

All efficacy endpoints defined in [Section 2.1.6](#) will be summarized descriptive by dose cohort and treatment group. For 6MWT results, descriptive summary will only be provided for those complete the 6 minutes walk test.

The mean composite scores between avalglucosidase alfa and alglucosidase alfa patients will be compared. The difference in average composite scores between avalglucosidase alfa and alglucosidase alfa patients will be used as the test statistic, and calculate a p-value. The null and alternative hypotheses for the primary efficacy endpoint are described as H_0 and H_a below:

H_0 : Mean Composite Score for avalglucosidase alfa = Mean Composite Score for alglucosidase alfa; versus

H_a : Mean Composite Score for avalglucosidase alfa \neq Mean Composite Score for alglucosidase alfa

The difference in average composite scores between avalglucosidase alfa and alglucosidase alfa patients will be used as the test statistic.

The control arm (alglucosidase alfa treatment) in Cohort 3 will serve as a reference. If deemed appropriate, these analysis might be repeated using Cohort 2 and/or Cohort 1 patients combined with Cohort 3 avalglucosidase alfa treated patients.

Statistical inference will be performed based on the re-randomization approach. Specifically, all possible randomization sequences that are consistent with the selected randomization design (i.e., stratified randomization stratifying on gender) will be generated, the test statistics will be calculated for all randomization sequences, and the statistical significance level will be calculated as the proportion of more or equally extreme scenarios than the observed one, among all possible scenarios. Due to the small sample size and open-label nature, p-values will serve as references only and any interpretations should be made with caution.

Similar re-randomization test might be performed for other efficacy endpoints.

Patient profile (in terms of change over time starting from baseline) will be generated for all efficacy parameters where each patient will serve as his/her own control. Effect of switching from alglucosidase alfa to avalglucosidase alfa will be assessed descriptively within each study cohort and treatment arm based on changes from pre-study (collected by retrospective chart review at screening/baseline) to 6 months (Week 25) post-avalglucosidase alfa treatment using descriptive statistics. Denominators for the percentages will be based on the safety population with evaluable data on the corresponding endpoint.

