Retrospective review of available assessments prior to study entry documents clinical decline or suboptimal clinical response. It may include the following assessments:

- Respiratory function evaluation:
 - FVC (% predicted),
 - use of ventilator support.
- Motor function evaluation:
 - gross motor milestone,
 - GMFM-88 composite score,
 - Pompe-PEDI mobility,
 - QMFT,
 - GMFCS-E&R,

- other test or assessment, if any.
- Cardiac Function Evaluation:
 - Left ventricular mass (LVM) standard score (Z-score);
 - Left ventricular mass index (LVMI; g/m²);
- Other Evaluation:
 - Presence of ptosis.

The above assessments have documented (at least 2 recent and consecutive assessments prior to study entry, not less than 2 weeks apart) evidence of clinical decline or suboptimal clinical response in at least 1 of the following parameters related to Pompe disease and NOT related to intercurrent illness as assessed by the Investigator, in addition to at least 1 previous assessment prior to onset of decline:

- For patients entering Stage 1 - clinical decline in at least 1 of the following parameters: respiratory function, motor skills, and/or cardiac parameters.
- For patients entering Stage 2 - suboptimal clinical response in at least 1 of the following parameters: respiratory function, motor skills, and/or presence of ptosis.

Growth parameters at baseline

Weight (kg), height/total body length (cm), body mass index (BMI, kg/m²), head circumference (cm) and Tanner stage of sexual maturation.

Vital signs

Vital signs include systolic blood pressure, diastolic blood pressure, heart rate, respiratory rate, temperature, and oxygen saturation. The baseline values for vital signs are the last non-missing assessment prior to the first study treatment by comparing the infusion time and measurement time.

Immunogenicity status

The immunogenicity evaluation at baseline includes antibody status (positive or negative) and magnitude (titer) of the anti-drug antibodies (ADA).

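### The SAP allows the composite comparison to be repeated with non-randomised Cohort 1 and 2 patients added to the avalglucosidase alfa arm, which confounds drug with stage and gains nothing from the randomisation

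*SAP*

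**What the plan says.** SAP section 2.4.8 sets a two-sided hypothesis on the mean composite score, takes the difference in arm means as the test statistic and calls for a p-value. It names the Cohort 3 alglucosidase alfa arm as the reference and continues that, where this is judged appropriate, "these analysis might be repeated using Cohort 2 and/or Cohort 1 patients combined with Cohort 3 avalglucosidase alfa treated patients". The next paragraph opens with "Statistical inference will be performed based on the re-randomization approach" and defines the reference set: "all possible randomization sequences that are consistent with the selected randomization design (i.e., stratified randomization stratifying on gender) will be generated". No separate method is given for the pooled version. The same section says that "p-values will serve as references only and any interpretations should be made with caution".

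Other places that bear on this:

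- **Who is randomised.** Only Cohort 3, 1:1 and stratified on gender, at least 10 patients (SAP 1.1, 2.2). Cohorts 1 and 2, at least 5 patients each, are assigned in sequence to 20 and 40 mg/kg.
- **Entry.** Stage 1 requires "clinical decline in at least 1 of the following parameters: respiratory function, motor skills, and/or cardiac parameters" (SAP 2.1.1). Stage 2 requires sub-optimal response in respiratory function, motor skills or ptosis, which are the three domains scored in the composite.
- **Scoring.** Table 1 (SAP 2.1.6) gives 2, 1 or 0 in a domain flagged at baseline and 1, 0 or -1 in one that is not.
- **Planned scope.** Protocol 11.4.3 places the comparison in the Cohort 3 mITT population. SAP 2.3.2 defines mITT as randomised Cohort 3 patients. SAP section 3 and protocol 11.4.3.1 each rely on there being a single hypothesis test.

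**The concern.** A re-randomisation test draws its force from the allocation that could have happened. No allocation could have put a Cohort 1 or 2 patient on alglucosidase alfa. Adding those patients to one arm only brings into the drug comparison whatever separates the stages: entry criteria, time of entry and, for Cohort 1, a dose that may not be the Cohort 3 dose.

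The scoring makes this concrete. A Stage 1 patient who entered on cardiac criteria alone, with no scored domain flagged, scores 0 if nothing changes. A Cohort 3 patient flagged in one scored domain scores 1 if nothing changes. The difference is one point before any drug effect.

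The wording allows three pooled versions (Cohort 1, Cohort 2, or both) and sets no rule for choosing among them. In an open-label trial the choice can be made after results are known. What is at stake is a pooled mean difference and p-value that could be read as extra evidence of efficacy.

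**Working it through.** The documents give no alpha, power, SD or reference-set size for the composite, so there is no planned figure to reproduce. Inputs from the documents: Cohort 3 with 10 patients split 5 and 5, and 5 or 10 Stage 1 patients added. Assumptions: nominal 5%, composite SD 1 point, stage shifts of 0 to 2 points, and gender splits of 6/4 or 8/2.

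**1. Bias of the pooled mean difference.** Let d be the difference in expected score between Stage 1 and Cohort 3 patients on avalglucosidase alfa. The pooled arm has mean (5·m + 10·(m + d))/15 = m + (10/15)·d, so the bias is two-thirds of d.

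- d = 0.5 gives 0.33 points; d = 1.0 gives 0.67 points.
- With 5 added patients the fraction is 5/10, giving 0.25 and 0.50 points.
- Illustration: everyone is unchanged, 5 of 10 Stage 1 patients entered on cardiac criteria alone with no flag, and everyone else has one flag. Then d = -0.5 and the bias is -0.33, against the drug. If Stage 1 patients carry more flags than Cohort 3, the sign reverses.

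**2. Reference set for Cohort 3 alone.** A 6/4 split gives C(6,3) × C(4,2) = 20 × 6 = 120 sequences, with smallest two-sided p 2/120 = 0.017. An 8/2 split gives 70 × 2 = 140 sequences and 2/140 = 0.014.

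**3. Pooled statistic, Cohort 1 and 2 labels held fixed.** Let a be the score sum of the treated Cohort 3 patients, S the sum over all ten and B the sum over the ten added.

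- Cohort 3 only: T = a/5 - (S - a)/5 = (2a - S)/5.
- Pooled: T = (a + B)/15 - (S - a)/5 = (4a - 3S + B)/15.

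Only a varies across sequences, and both statistics increase in a. The sequences are therefore ranked identically and the one-sided p-value is the same. The pooled reference distribution is centred at (B - S)/15, two-thirds of the observed stage difference, rather than at zero. A two-sided p based on absolute values can therefore differ, but only because of that offset.

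**4. Pooled statistic, labels permuted over all patients.** There are C(15,5) = 3,003 arrangements with 5 added and C(20,5) = 15,504 with 10 added. The permutation treats the added patients as exchangeable with controls, which the design does not provide.

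**5. Simulated type I error with no drug effect** (3,000 replicates per setting, 6/4 split, integer scores, 999 random permutations for the all-patient version):

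| Stage shift (either sign) | All labels permuted, 5 added | All labels permuted, 10 added |
|---|---|---|
| 0 | 0.033 | 0.038 |
| 0.5 | 0.041–0.046 | 0.050–0.057 |
| 1 | 0.054–0.068 | 0.130–0.131 |
| 2 | 0.121–0.128 | 0.346–0.359 |

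Across the same settings the fixed-label version stayed at 0.017–0.027 and Cohort 3 alone at 0.016–0.024. The one-sided p-values of those two agreed in every replicate, as step 3 requires.

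A second simulation used Table 1 scoring directly, with 10 added patients, change probabilities of 0.15/0.70/0.15 per domain and a mean of 1.25 flagged domains in Cohort 3 (1,500 trials). All-patient permutation rejected in 5.9%, 3.9%, 5.2% and 11.6% of trials for flag differences of -0.5, 0, 0.5 and 1.0. The last case is extreme: it needs 2.25 of 3 domains flagged on average in Stage 1, where ptosis is not an entry criterion.

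**The case against.** A reader might infer that no valid reference set exists once Cohorts 1 and 2 are added. The SAP does not support that. It limits the sequences to those consistent with the gender-stratified design. Read literally, this re-randomises Cohort 3 only and leaves the added labels fixed, and that test keeps its size. A reader might also infer that the SAP prescribes an inflated test. It does not: the inflation belongs to permuting everyone, which is not specified, and needs a shift near one point with 10 patients added. Nor can one infer that pooling favours the drug, since the direction is unknown.

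The repeat could also be read as covering only the comparison of means, because the inference paragraph comes after it. However, the sentence directly follows the hypotheses and the test statistic, and no other inference is offered, so the test is at least permitted.

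The strongest mitigation is status. The composite is exploratory (SAP 1.5), the primary objective is safety, the repeat is doubly conditional, p-values are for reference, and SAP 2.4.8.1 disclaims confirmatory use and multiplicity adjustment. This stands and lowers the severity. It does not remove the confounding: the caution is attributed to small sample size and open-label conduct, and a biased mean difference remains biased whatever is said about its p-value.

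**Conclusion.** The concern holds as a minor point. The pooled mean difference confounds drug with stage by two-thirds of any stage shift when 10 patients are added to 5. The added patients contribute no randomisation-based evidence: depending on the implementation, the one-sided p-value simply repeats the Cohort 3 result, or it rests on unsupported exchangeability, with type I error of about 12–13% at a 1-point shift. At a shift of 0.5 the error rate stays close to nominal, and the bias in the mean is the main harm.

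The algebra depends only on the group sizes. The error rates depend on the assumed SD, shifts, gender split and alpha, none of which the documents give.

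The permission also sits badly with the Cohort 3 mITT scope in protocol 11.4.3 and the single-test statement in SAP section 3. SAP 1.6 records the extension of the composite to all patients but not a pooled comparison.

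**What to change.** Replace the sentence in SAP 2.4.8 with: *Cohorts 1 and 2 will be shown descriptively by cohort alongside Cohort 3; the re-randomisation test and any p-value are restricted to randomised Cohort 3 mITT patients.*

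This matches the protocol and the mITT definition. Descriptive efficacy summaries for all cohorts are already planned (SAP 2.4, protocol 11.4.3), so no data display is lost. The cost is one sentence and an optional p-value.
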